D2C is a structural intervention designed to sustainably change the HIV care providers' practices and facilitate information exchange at the facility level. To address the implementation science questions by measuring the provider-level outcomes and avoid contamination of the control condition due to unblinded allocation of intervention at the patient level, we propose a cluster-randomized trial design for this pilot study and the prospective RCT. We will select eligible HIV clinics (see "Study Sites," above) and randomly assign them 1:1 either to the intervention or the control arms. To achieve greater comparability between the arms, we will match pairs of eligible sites based on organizational context factors derived from Aim 1 data analysis, including facility size and type (e.g., NGO vs. public clinic), service delivery structure (e.g., social workers vs. nurses), and existing services for HIV-positive PWID (e.g. Steps Toward Health) and will randomize within the pairs. This will minimize the degree of between-cluster variation within the groups and increase power and precision.

Randomization will be conducted by the data manager using a computer program.

Sample size

We used methodology from Hayes et al⁸⁴ to determine the effect size that the intervention needs to demonstrate in a feasible matched-pair randomized trial. We assumed the cluster size of 75 patients (based on the optimal case manager workload) with 5 clusters per arm (potentially manageable number given the existing research infrastructure in Ukraine), coefficient of variation between clusters within matched pairs equal to 0.15 (empirically estimated based on the data from 56 clinics in the ART OPTI study, see Previous Studies), power of 80% and 0.05 significance level. Proportion of participants re-engaging into ART within 3 months after inclusion into the study was used as the key outcome. Under the assumptions, the relative difference between the study arms should be at least 22% (e.g. 50% vs 72%). The adjacent chart shows the power and sample size of a pilot trial needed to detect this difference with 0.05 significance level. To achieve 80% power, we will need to recruit 160 participants, or 80 per arm. We propose to divide the sample equally between 4 sites (2 per arm) to test the matching procedures. We do not adjust for loss-to-follow-up because for our main outcomes (ART initiation, viral suppression), loss to follow-up is equal to not achieving the outcome.

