Intervention Overview

Clinics randomized to the intervention arm will implement the D2C strategy as described above, including Health Data Information, Active Surveillance, and Case Management with the addition of the data component. The D2C strategy will involve a 5-step process: (1) identify not-in-care PLWH using the MIS, (2) verify eligibility criteria, (3) contact patients and invite to visit the clinic, (4) determine care status and reengage into care, and (5) provide case management services and confirm engagement in care.¹²

D2C Ukraine

Steps 1 and 2 will follow the same procedure at both intervention and control sites to ensure equal conditions of study enrollment. Step 3 will be conducted using Active Outreach at the intervention sites. Steps 4 and 5 will be achieved through use of an Acuity Tool and derived Acuity Score. The Acuity Tool will be used to identify barriers to HIV care engagement, including mental health and substance abuse, and to establish referrals to other services, as described above in Overview of Data to Care Strategies.

Procedures

Patient selection and verification of inclusion criteria

A Recruiter (clinical staff authorized to access MIS at each site) will use the D2C module in the MIS to access the “Tracking Journal” which includes patients who have a confirmed HIV diagnosis, started ART, and missed their clinical appointments (medication pick-up or other). Going through the list ('New cases' or 'In progress' or 'Not tracked' sections), Recruiter reviews the MIS data (including in other modules) and identify patients who meet the following criteria:

- a) registered within the MIS as having received a positive HIV diagnosis at any time in the past
- b) missed a clinical visit (ART pick-up or other) more than 7 days ago
- c) registered with IDU as probable mode of HIV transmission, or history of IDU documented at any clinical visit
- d) not been contacted by other clinical staff after the current missed visit
- e) 18 years or older

For each patient meeting these criteria, Recruiter puts an “E” letter in the beginning of the Comment field in the Tracking Result section (before any other text in this field, separated by a space). This letter indicates that the patient is eligible for recruitment into the study and filters the Tracking Journal to display only these patients.

Patient outreach and verification of exclusion criteria

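### The site Recruiter knows the clinic's arm, and the protocol sets no contact order or stopping rule for 40 patients per site, so identical written steps do not by themselves secure equal enrolment at listing and first contact

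*Combined protocol and SAP*

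**What the plan says.** **Allocation.** Under Study Design, clinics are matched in pairs and the investigators will "randomly assign them 1:1 either to the intervention or the control arms". The only sentence on mechanics is "Randomization will be conducted by the data manager using a computer program". Nothing is said about concealment, or about whether patients are listed before or after sites learn their arm.

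**Size.** Under Sample size, "we will need to recruit 160 participants, or 80 per arm", and "We propose to divide the sample equally between 4 sites (2 per arm) to test the matching procedures".

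**The safeguard.** Intervention Overview lists five steps. Step 1 identifies patients in the MIS, Step 2 verifies eligibility, and Step 3 is contact and invitation. It then states: "Steps 1 and 2 will follow the same procedure at both intervention and control sites to ensure equal conditions of study enrollment".

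**Who applies it.** Under Patient selection and verification of inclusion criteria, the Recruiter is clinical staff at the site. The instruction reads "Going through the list ('New cases' or 'In progress' or 'Not tracked' sections), Recruiter reviews the MIS data (including in other modules". It ends with an E flag in the Comment field for each patient who meets five criteria. Two of these turn on reading the record: a documented history of injecting at any visit, and no contact by other staff since the missed visit.

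**First contact.** Under Patient outreach and verification of exclusion criteria, the same Recruiter phones the flagged patients under the Public Health Center's Tracking SOP, judges the exclusions, and invites them with a script that has one version per arm. At intervention sites only, the Recruiter also exports the ER-list (patients not reached, or refusing to attend) for a Case Manager. Consent comes later, at the first visit.

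**The concern.** In a cluster trial every patient at a clinic has the same arm. If the person who finds and invites patients knows that arm, allocation is not concealed at the point where it matters. Using the same criteria in both arms governs what is written down. It does not govern how an arm-aware person reads an ambiguous record, or whom that person calls first.

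The eligible pool is wide: any visit missed by more than 7 days qualifies, so it can run from a short lapse to a long absence. Such patients plausibly differ in their chance of returning, attending and being suppressed. With two clinics per arm, a difference between arms in who is invited goes straight into the arm contrast. From there it reaches the 22-point feasibility rule under Statistical Analysis and Feasibility Assessment, and the effect size that the pilot is meant to supply for the later trial.

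**Working it through.** **1. The plan's own figure.** Inputs from Sample size: 50% against 72%, "power of 80% and 0.05 significance level", 80 per arm. Exact power of the two-sided Pearson test at 80 per arm is 81.6% (pooled normal formula 82.0%). The two-sided formula needs 76 per arm (152 in total), or 85 (170) with continuity correction. The stated 160 is therefore consistent with an individual-level calculation, rounded up, with no allowance for clustering. Divided over sites: 160 / 4 = 40 per site.

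**2. Does the Recruiter know the arm?** No sentence says so. It follows from three facts: allocation is by clinic, the Recruiter's script is arm-specific, and only intervention Recruiters hand over an ER-list.

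**3. Where discretion remains.**

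| Stage | What the text fixes | What it leaves open |
|---|---|---|
| Listing (Steps 1 and 2) | Flag every patient who meets the criteria; flags sit in the MIS | Reading records for injecting history and prior staff contact |
| First contact (Step 3) | Phone the flagged patients under the Tracking SOP | Order of calls |
| Reaching 40 | Equal split over four sites | When enrolment stops if more are eligible |

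**4. How far enrolment could be skewed.** Study Sites requires at least 150 registered patients with injecting as mode of transmission; 40 / 150 = 27%. This is only a loose guide, because the number with a missed visit who can be reached and will consent is not given. Suppose half of a site's enrollable patients have the better prognosis. Drawing 60%, 70% or 80% of 40 from that half needs 24, 28 or 32 such patients, hence a pool of at least 48, 56 or 64. With a pool of 40 no shift is possible.

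**5. Size of a false difference (assumptions, not estimates).** Bias = (share from the better half in one arm − share in the other) × (success rate in the better half − rate in the worse half). The other arm is taken to draw evenly (0.5), and the mean rate is 50%.

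| Rates, better/worse half | Share 60% | Share 70% | Share 80% |
|---|---|---|---|
| 60% / 40% | 2 points | 4 | 6 |
| 65% / 35% | 3 points | 6 | 9 |
| 70% / 30% | 4 points | 8 | 12 |

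For example, (0.7 − 0.5) × (0.65 − 0.35) = 0.06. The sign reverses if the intervention sites are the ones drawing harder cases.

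**6. Effect on a 22-point rule.** Assume control 50%, a true effect of 15 points, and a bias of 6 points in favour of the intervention.

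- Ignoring clustering: SE = √[(0.25 + 0.65×0.35)/80] = 0.0773, so P(observed ≥ 22 points) = P(Z ≥ 0.07/0.0773) = 18%. With 71% in the intervention arm, SE = 0.0755 and P = P(Z ≥ 0.01/0.0755) = 45%.
- Adding the plan's coefficient of variation of 0.15 with two clusters per arm and no gain from pairing, the variance rises by 0.15² × (p₀² + p₁²)/2. The SEs become 0.116 and 0.119, and the probabilities 27% and 47%.

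The rise is 26 points in the first version and 19 in the second. The 50% rate belongs to ART re-engagement within 3 months, whereas the 22-point rule is set for engagement in HIV care, for which no control rate is given. These probabilities are therefore illustrative only.

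**The case against.** The strongest reply is that listing is meant to be exhaustive. The Recruiter is told to flag every patient who meets the criteria, those criteria are mostly facts in the record, and flags, statuses and phone contacts are logged in the MIS, so selective listing would leave a trace. This stands, and it narrows the point. A reader might infer that the Recruiter may choose freely whom to list; the text does not support that.

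By the protocol's own numbering, call order belongs to Step 3, so the equal-procedure sentence does not strictly cover it. That too stands, but then no stated safeguard covers it.

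A reader might also infer that Recruiters phone until 40 are enrolled, that no call order exists anywhere, or that listing is known to follow randomisation. The protocol states none of these. Contact is delegated to the Tracking SOP, which is not among the documents and may fix an order.

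The analysis adjusts for sex/gender, age and baseline covariates that vary across sites, and examines substance use severity and ART history. This could remove part of a selection effect. It cannot remove the unmeasured part, and pair indicators and site intercepts do not correct a shift common to an arm.

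Finally, the section on protection against risks says that a social worker recruits, not clinical staff. The two descriptions should be reconciled, but either person would know the site's arm.

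**Conclusion.** The point holds in limited form. The person who reviews records, flags patients and makes first contact must know the clinic's arm. The protocol text fixes neither a contact order nor a rule for arriving at 40 per site. The claim of equal enrolment conditions is therefore not supported for listing and first contact.

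The documents do not show that selection will occur, which way it would run, or how large it would be. It is near nil where a site has only about 40 enrollable patients. With a larger pool, and on the 65%/35% assumption, a shift to 60–80% from the better half gives 3 to 9 points in either direction, of which covariate adjustment would remove only part. The step from 18% to 45% should not be read as the trial's actual risk: it ignores clustering, assumes a 15-point true effect, and borrows its control rate from a different outcome. This is a cheap improvement worth making, not a defect that invalidates the design.

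**What to change.** 1. Have the Data Manager generate the candidate list with one MIS query, run identically at all four clinics, for the criteria held as MIS fields. Do this before the allocation is released to sites where possible, and add later cases in weekly batches.
2. Attach a computer-generated random order for the study invitation to the list and to each batch. Recruiters follow it until 40 are enrolled, and record in the existing Comment field a reason for each listed patient judged ineligible or passed over.
3. Let routine tracking of missed visits continue under the Tracking SOP. If that SOP already fixes an order, reconcile the two. Say also how a listed patient is handled when routine tracking reaches them before their turn, since prior contact by other staff is itself an eligibility criterion.
4. Report counts listed, contacted and enrolled, and time since the missed visit, by arm.
5. Limit the Intervention Overview claim to what this rule protects. Step 3 outreach still differs by arm before consent, because intervention Case Managers make additional recruitment efforts.

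The change uses the existing MIS module, Data Manager and Comment field, and leaves sample size and eligibility as they are. The cost is slightly less Recruiter freedom over invitation order and some extra data handling. Judgement remains on criteria not held as MIS fields.

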The patients on the EL-list should be instructed to notify Recruiter and/or Case Manager before coming to the clinic, to expedite the visit procedures. If a patient from the EL-list comes to the clinic without notifying Recruiter or Case Manager, a receptionist should notify Recruiter and direct the patient to see them.

After meeting the patient, Recruiter conducts (or refers to) regular clinical visit procedures, refers the patient to Interviewer, and changes the E-status to "E(R)S". Interviewer conducts the Informed Consent procedure according to the study-specific SOP and using the consent form (Annex 3), and in case of consent performs baseline interview (see below). At the Control sites, Interviewers fill out the Contact Information Form (Annex 5) to enable tracking for follow-up interviews.

After the interview, the patient comes back to Recruiter, who makes referrals to available care and support services (Standard of Care sites) or introduces the patient to Case Manager (Intervention

sites). At the Intervention sites, Recruiter fills out the top section of the Case Management Checklist (Annex 4) and gives it to the Case Manager together with the patient.

Case Manager may conduct the first intervention session on the same day or schedule a meeting with the patient at the earliest convenience.

[figure not shown]

Figure. Patient status update workflow

Intervention Procedures

The case-management component will be implemented according to a Manual, developed by the study team. Briefly, the content and intensity of case management will be based on an overall Acuity Score across domains. Case Managers will assess clients every 3 months to determine the treatment plan and record this information in the Case Management forms to enable progress monitoring. Care teams of nurses, case managers, and outreach specialists will coordinate holistic wrap-around care to meet the social service and health needs of out-of-care patients, many of whom face substance abuse and mental health barriers to HIV care. Case managers will develop client-centered service plans based around “SMART” objectives (**S**pecific, **M**easurable, **A**chievable, **R**elevant, **T**ime-limited).

Case Managers will schedule new clients for intake appointments and work with clients to develop treatment plans. Specific duties include:

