- use Acuity Tool to assess patient-identified financial, socioeconomic, and housing profiles and provide comprehensive internal or external referrals for supplemental or long-term resources;
- develop and implement personalized treatment plans for all clients based on the acuity assessments through existing case management programs;
- ensure accurate tracking and documentation of all interactions and activities with patients using the acuity tool and Tracking Module within the MIS;
- establish, develop, and maintain professional relationships with diverse treatment and service providers, including AIDS care, primary care, substance use, mental health, and social services;
- maintain current contact information using the Contact Information Form (Annex 0) and updates it at each visit.

Additionally, Case Managers assist Interviewers to schedule follow-up interviews (see below) in conjunction with the Intervention sessions (at 6 and 12 months).

Control Condition

Clinics randomized to the standard of care arm will continue to implement their client identification processes and case management as usual. One of the most common interventions with a focus on PWID is Steps Toward Health,⁸⁵ a case management program developed and tested through the PEPFAR-funded RESPOND project.^{8,86} It is theory-driven and standardized in manuals that contain background information, logic models, client assessment worksheets, step-by-step instructions for each session, and monitoring and evaluation guidelines. This 5-session intervention includes modules on self-care, HIV transmission risk reduction, drug treatment, and ART adherence. It does not include active outreach, client tracking, or tailored treatment components. Other possible interventions include Community-based Retention Intervention, Patients' School, and others.

Provision of these interventions (the fact of enrollment) will be recorded in the MIS by Recruiter, but the actual process data will not be collected.

Data Collection

Data on **primary outcomes** will be obtained from clinical records in the MIS and absence of data will be equal to not achieving the outcome, therefore the effective sample size will be exactly 160 patients. Data from the MIS will be extracted monthly (Annex 6). The primary outcomes are defined as:

- Engagement in HIV care: at least 3 clinical visits over at least 6 months within 12 months after study enrollment.

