- ART (re-)initiation: initiating or re-initiating ART within 3 months after study enrollment.
- ART adherence: the percentage of days in possession of medication (pharmacy refill gap method)⁸⁷
- HIV Viral Suppression: having at least one VL test with <200cp/ml and none with >=200cp/ml within 12 months after study enrollment.

Data on **secondary outcomes** will be collected using the patient survey at baseline, 6 and 12 months after enrollment. The secondary outcomes will include items in the following domains:

- Substance Use: Substance use battery from the Ukrainian IBBS studies, AUDIT-C; DAST-10 scale for addiction severity.
- Trust in Physician Scale
- Substance Use & HIV Stigma Mechanism Scales
- Readiness for Drug Treatment Scale
- Mental Health: PHQ-9
- Risk behaviors: Risk Behavior Assessment (RBA), modified for the drug use patterns of PWID in Ukraine. The RBA assesses drug use and sex-related HIV risk behaviors.
- Quality of life: Short Form-12 (SF-12), a global measure of patient quality of life; HRQoL, HIV-related quality of life
- Medical co-morbidities and engagement in ancillary care: (OAT, TB, STI and Hepatitis treatment) by self-report.

- HIV Treatment Satisfaction Questionnaire
- Patient-side cost questionnaire
- Socio-demographic information, including age, housing status, sex/gender, family/marital status, income, education, employment status.

The surveys will be administered by an experienced Interviewer, hired at each site. The questionnaire will be programmed using REDCap platform installed on a UIPHP server.

Intervention implementation

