We have powered this pilot study to evaluate feasibility of a prospective cluster RCT. The RCT will be considered feasible if the difference in the proportion of patients achieving the primary outcome (engagement in HIV care) will reach 22% between the study arms. We will estimate the impact of the intervention on the HIV care continuum using mixed effects models. For all outcomes, the data will have the same structure, with observations (t) nested within participants (i) nested within sites (j) nested within matched pairs (k). The correlations among observations will be addressed by using fixed-effects indicators for matched pair and normally distributed random intercepts for sites and for participants. Our mixed-effects models will include indicators for each of the two follow-up assessments, an indicator for site group assignment, and two group-assignment-by-follow-up interaction terms. We will also include sex/gender, age, and baseline covariates that have been identified in preliminary analyses as varying significantly across sites. A logit link function will be used for the primary outcome of ART (re-)initiation (defined above), and the coefficients for the two group-assignment-by-follow-up interaction terms will provide the estimates of the subject-specific intervention effects at 6 and 12 months post-baseline. We will examine the effects of sex/gender, age, substance use severity, ART history at baseline and other covariates in the multivariable models.

We will characterize patterns of behavior that impact HIV transmission (episodes of syringe sharing and episodes of unprotected intercourse in the prior 30 days without viral suppression) and we will use the same mixed-effects approach described above but with a log link function and negative

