We will use the **Consolidated Framework for Implementation Science adapted for complex systems (CFIR-CS)** to guide implementation evaluation of the D2C strategy.^{15,105,106} Key aspects of the D2C intervention are that it covers multiple settings (i.e., patients must access and interact with providers in many different health care sectors), its success depends on interactions and communication between organizations (e.g., between case managers, addiction treatment specialists, and HIV treatment providers); and it uses multiple types and sources of data to identify patterns in services and outcomes that will be used to improve or modify practices. The CFIR-CS organizes implementation factors into 5 domains: **intervention characteristics** (accuracy of data, timeliness of data sharing with partner agencies, development of practice change action plans based on data), **organizational characteristics** (integrating D2C strategy into existing protocols, agency-wide buy-in, commitment to D2C strategy), **providers' roles and characteristics** (case managers' previous experiences, attitude toward the use of data in care provision, relationships with other medical and social service providers, time and resources devoted to providing case management for PLWH), **patients' roles and characteristics** (type of medical and social needs, level of need), and **implementation processes** (participating in the monitoring and practice improvement process, using MIS data to inform practice change). The implementation of the D2C strategy is affected by the **external context** in which these organizations and their staff operate (economic, social, and political factors that may affect implementation process such as MAT "slot" and psychosocial support service).

Measures of implementation are the intermediary outcomes¹⁰⁷ that describe how well the implementation was carried out and include use of the acuity tool with new and returning clients, and use of data generated from acuity tool and MIS to modify practices, documentation of patient visits and contacts. Implementation influences **outcomes**, which include patient outcomes (viral load, appointment kept); provider outcomes (uptake, consistent use, patient contact, outreach efforts, time spent with patients); and processes of care (recruitment rate, extent to which intervention tracks patients and follows up on and coordinates tests, referrals, and care across organizations, settings, and acuity tool domains).

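### Viral suppression is scored from routine tests with an absent test counted as failure, so the arms can differ through testing alone, and no planned analysis separates testing from suppression

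*Combined protocol and SAP*

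**What the plan says.** Viral suppression is one of the primary outcomes. Under Data Collection it is defined as "having at least one VL test with <200cp/ml and none with >=200cp/ml within 12 months after study enrollment". The data come from "clinical records in the MIS and absence of data will be equal to not achieving the outcome", and the plan concludes that the effective sample is exactly 160. The Sample size section applies the same logic to viral suppression by name, to justify making no allowance for dropout: "loss to follow-up is equal to not achieving the outcome".

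No VL draw is scheduled for the study in the supplied text. At the first visit the recruiter "conducts (or refers to) regular clinical visit procedures", with no VL specified. The fixed study assessments are surveys: the secondary-outcome data "will be collected using the patient survey at baseline, 6 and 12 months after enrollment".

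Specific Aim 3a lists, among the processes of care to be assessed, the "extent to which intervention tracks patients and follows up on and coordinates tests, referrals, and care across organizations". On the control side, "Clinics randomized to the standard of care arm will continue to implement their client identification processes and case management as usual".

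The Statistical Analysis section plans a second set of outcome analyses by multiple imputation under missing at random. It also defines a transmission-risk measure, "episodes of syringe sharing and episodes of unprotected intercourse in the prior 30 days without viral suppression", which supplies inputs to the cost-threshold analysis.

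**The concern.** Scored suppression combines two things: having a VL on record, and that VL being below 200. Failure coding is often defended as conservative. That defence works when results are equally likely to be absent in both arms, or when patients without a result really are unsuppressed. Here testing is left to routine care in both arms, and the intervention is a tracking and coordination strategy that may raise testing. A control patient who is on ART and suppressed, but has no VL in the window, counts the same as a patient with virological failure.

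A difference in testing could therefore be reported as a virological benefit and used in planning the larger trial. If the same coding is carried into the transmission measure, untested patients would be treated as infectious. The plan does not say how untested patients are classified there. The ordinal care-continuum model is exposed in a similar way, because its last two stages differ only in whether there is evidence of suppression.

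**Working it through.** **The plan's own figure.** The Sample size section gives 160 participants (80 per arm) for 80% power at 0.05 to detect 50% against 72%. Taking the test as two-sided (sidedness is not stated), the pooled normal formula is

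n = [1.96·√(2·0.61·0.39) + 0.84·√(0.5·0.5 + 0.72·0.28)]² / 0.22² ≈ 76 per arm.

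At 80 per arm the power is 82.0% by normal approximation and 81.6% exactly (uncorrected chi-square). The stated figure reproduces as an individual-level calculation without clustering. It was computed on ART re-engagement, so the present point does not change it.

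**Inputs for the artefact.**
- True suppression s, equal in both arms. Two anchors come from the Background: 28% of HIV-positive PWID suppressed, and about 74% of PWID on ART undetectable. A middle value of 50% is assumed.
- Share with at least one VL on record: t₀ in control, t₁ in D2C. The documents give neither, so both are assumed.

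**One test per tested patient.** An arm's scored suppression is s·t, so the spurious difference is s·(t₁ − t₀). For 70% against 90%:
- s = 28%: 0.28·0.70 = 19.6% and 0.28·0.90 = 25.2%, a difference of 5.6 points.
- s = 74%: 0.74·0.70 = 51.8% and 0.74·0.90 = 66.6%, a difference of 14.8 points.

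| Assumed coverage, control vs D2C | s = 28% | s = 50% | s = 74% |
|---|---|---|---|
| 80% vs 90% | 2.8 | 5.0 | 7.4 |
| 70% vs 90% | 5.6 | 10.0 | 14.8 |
| 60% vs 90% | 8.4 | 15.0 | 22.2 |

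With 80 per arm and clustering ignored, the middle row would be significant at 0.05 with probability 13%, 25% and 48%.

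**What s stands for.** Failure coding removes from each arm the untested patients who are truly suppressed. The rate that matters is therefore suppression among the untested. If it is u in both arms, the artefact is u·(t₁ − t₀). If every untested patient is unsuppressed, u = 0 and there is no artefact.

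**Repeat tests.** The definition also requires that no VL be 200 or more. Let the number of tests be Poisson with mean μ.
- If results within a patient are independent with probability s of being below 200, scored suppression is exp(−μ(1−s)) − exp(−μ). At s = 74%, means of 0.7 vs 1.5 give 33.7% vs 45.4% (+11.7 points), but 1.5 vs 3.0 give 45.4% vs 40.9% (−4.5 points).
- If each patient is always suppressed or never suppressed, scored suppression is s·(1 − exp(−μ)). The same pairs give 37.3% vs 57.5% (+20.2) and 57.5% vs 70.3% (+12.8).

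So the sign depends on how much testing there is and how much results vary within a patient.

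**Does the planned imputation separate the two?** Imputation needs missing values. The Data Collection rule turns every absent VL into an observed failure and fixes the sample at 160, so there is nothing to impute for this outcome. No planned analysis reports VL coverage by arm or suppression among those tested.

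**The case against.** The case on the other side has several parts.

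- **An effect on testing is not shown.** The Aim 3a phrase belongs to a list of things to be measured. It is not a procedure and does not name VL, and the case managers' duties include no ordering of VL. This stands as a limit: the text makes a testing difference plausible but does not establish one. It is plausible because the MIS summary for case managers includes viral load and intervention sites review MIS benchmark reports each quarter.
- **Control clinics may also follow up tests.** A reader might infer that they have no such function. The documents do not say so. Every site must already provide case management, the lack of client tracking describes one programme (Steps Toward Health), and a retention intervention is among the others named. A difference in intensity is enough for the concern.
- **The direction is not fixed.** Patients enter after a missed visit, so an early test may come back high and fail the patient for the whole window. This stands, as the repeat-test figures show.
- **Untested patients may truly be unsuppressed.** Many may be out of care, and better testing may partly be better retention, which is a real effect of D2C. This stands; the artefact is only the part due to testing among comparable patients.
- **The plan has a missing-data analysis.** It does, but as written it does not reach this outcome. Clarifying it is a large part of the remedy.
- **The text is incomplete.** The MIS extraction annex and the case-management manual are not in the supplied material, so the statement that no study VL is scheduled rests on what is supplied.

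**Conclusion.** The concern holds as a gap in the analysis plan. With failure coding and no common VL measurement, the arms can differ in scored suppression when true suppression is equal, and nothing planned would reveal it. For an assumed coverage of 70% vs 90% the artefact is 5.6 to 14.8 points, on the further assumptions of one test per tested patient and equal suppression among tested and untested patients. Its actual size cannot be computed from the documents.

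Two stronger readings are tempting and not supported. One is that any D2C gain in suppression would be only more testing. The sign is uncertain, and some of a testing gap may be real retention. The other is that the artefact threatens the 22-point feasibility criterion, because a coverage gap of about 30 points at s = 74% gives 22 points. That criterion is set on engagement in HIV care, so it is untouched.

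**What to change.** Keep failure coding as the main analysis. Add to the Statistical Analysis section, for viral suppression:

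1. By arm, the share of patients with at least one VL in the 12-month window, and the number of VL tests per patient.
2. Suppression among those tested, by arm, as a descriptive figure.
3. A statement that the planned multiple imputation treats an absent VL as missing rather than as failure. The imputation model should include arm, ART possession from MIS refill records, and visit records. Untested patients without ART stay failures.

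The suppression rate should not be pooled across arms in step 3, because that can shrink a real effect. Suppose all patients hold ART, true suppression is 60% vs 80% and coverage is 60% vs 90%. Failure coding gives 36% vs 72%. The pooled rate among those tested is (0.36 + 0.72)/(0.60 + 0.90) = 72%. Filling in with it gives 0.36 + 0.40·0.72 = 64.8% vs 0.72 + 0.10·0.72 = 79.2%, which is 14.4 points where the truth is 20.

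If step 3 and the failure-coded result differ materially, report the suppression difference as partly due to testing rather than as purely virological. Run the transmission inputs under both codings as a sensitivity analysis.

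The cost is a little more analysis, with no new visits, on MIS data that are already to be extracted monthly. The drawback is that the reported suppression effect may be smaller or less certain.
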